#### **4. SAMPLE SIZE JUSTIFICATION**

Patients will be enrolled until there are 120 patients in the CRABC m-MITT Population in Part A. The study will have 80% power to demonstrate non-inferiority between Group 1 and Group 2 using a 20% non-inferiority margin and a 2-sided 95% CI. This assumes a mortality rate in the comparator group (Group 2) of 41% and in the ETX2514SUL group (Group 1) of 36%. To have 120 patients in the CRABC m-MITT Population, Part A will need to enroll approximately 200 patients, assuming 60% of ABC clinical isolates are carbapenem-resistant. Patient enrollment in Part B (Group 3) will continue until Part A enrollment in the CRABC m-MITT Population is complete. Rates of carbapenem resistance among isolates from Part A patients will be monitored by the unblinded data manager/designee at the Clinical Research Organization on an ongoing basis.

#### **5. EFFICACY ENDPOINTS AND ASSESSMENT**

##### **5.1. Primary Efficacy Endpoint**

The primary efficacy endpoint for the study is 28-day all-cause mortality in the CRABC m-MITT Population in Part A.

##### **5.2. Secondary Efficacy Endpoints**

The secondary efficacy endpoints for Part A and Part B include the following:

- 28-day all-cause mortality in the Intent-to-Treat (ITT) Population;
- Clinical cure at TOC in the CRABC m-MITT Population;
- Clinical cure at TOC in the m-MITT, Clinical Evaluable (CE), Microbiologic Evaluable (ME), and CRABC ME Populations;
- Clinical cure at EOT, and LFU in the m-MITT, CRABC m-MITT, CE, ME, and CRABC ME Populations;
- Microbiological favorable assessment at EOT, TOC, and LFU in the m-MITT, CRABC m-MITT, ME, and CRABC ME Populations;
- 14-day all-cause mortality in the CRABC m-MITT and m-MITT Populations;
- 28-day all-cause mortality in the m-MITT and CRABC ME Populations; and
- PK exposure of ETX2514 and sulbactam in the PK Population.

##### **5.3. Other Efficacy Endpoints**

The exploratory efficacy endpoints include the following:

- Clinical cure based on MIC distribution of ETX2514SUL;
- Clinical cure based on MIC distribution of colistin;
- Clinical cure based on baseline resistance to ETX2514SUL, carbapenems, or colistin;

- Microbiologic favorable assessment based on MIC distribution of ETX2514SUL;
- Microbiologic favorable assessment based on MIC distribution of colistin;
- Microbiologic favorable assessment based on baseline resistance to ETX2514SUL, carbapenems, or colistin;
- Number of days in the intensive care unit;
- Number of patients transferred to the intensive care unit;
- For patients with VABP, VP, or ventilated HABP, number of days on ventilators;
- Number of days in the hospital; and
- Number of days on study drug treatment.

#### **5.4. Assessment of 28-Day Survival**

Every attempt must be made to record survival status at Day 28 or anytime thereafter for all randomized patients (including HABP/VABP/VP patients who are randomized to Part A based on a positive BPP rapid test, but who subsequently do not have growth of ABC in their respiratory sample culture), regardless of their status of treatment, as long as the patient has not withdrawn consent from participation in the study. An in-person assessment is preferred; however, this assessment may also be performed via a telephone call if an in-person visit is not possible.

For patients with an LFU Visit occurring before Day 28, a telephone call to assess survival will be made on Day 28 or anytime thereafter.

#### **5.5. Efficacy Assessments**

##### **5.5.1. Clinical Outcome**

Clinical outcome will be used to determine a response of clinical success for all patients. Based on the assessment of signs and symptoms, the Investigator will choose 1 of the following clinical outcomes at the Day 5, Day 7, EOT, TOC, LFU and ET Visits, if applicable. In Part A, in addition to the unblinded Investigator, a blinded assessor will also determine clinical outcome. If there is a discrepancy between the assessment of the blinded assessor and unblinded Investigator, the assessment from the blinded assessor will be used. If there is a missing assessment from either the blinded assessor or unblinded Investigator, the other available assessment will be used. An adjudication committee may be organized for endpoint adjudication should it be deemed necessary by the DSMB. In such a case, a charter will be developed that describes their activities.

**Clinical cure:** complete resolution or significant improvement of signs and symptoms that were present at baseline and no new symptoms, such that no additional Gram negative antimicrobial therapy is warranted.

**Clinical failure:** symptoms present at study entry have not significantly improved or completely resolved, or new symptoms have developed and require the initiation of a non-study Gram negative antibacterial drug therapy, death, or intolerance to study drug leading to discontinuation from the study treatment.

**Clinical indeterminate:** determination cannot be made because of missing data or the patient is lost to follow-up.

## 5.5.2. Microbiologic Outcome

### 5.5.2.1. Microbiologic Outcome for Bacteremia, Complicated Urinary Tract Infection, or Acute Pyelonephritis

For patients with bacteremia, complicated urinary tract infection (cUTI), or acute pyelonephritis (AP), per-patient microbiological response will be determined programmatically as 1 of the following outcomes based on the results of blood and/or urine cultures at EOT, TOC and LFU Visits. A microbiological favorable assessment will include eradication and presumed eradications, as detailed below.

#### Microbiologic eradication:

- For patients with cUTI or AP: the baseline strain of ABC is reduced to  $<10^3$  colony-forming units (CFU)/mL on urine culture and negative on repeat blood culture (if positive at baseline), or
- For patients with bacteremia: absence of the baseline strain of ABC on culture.

Microbiologic presumed eradication: no culture was done, and the patient meets clinical criteria for clinical cure.

#### Microbiologic persistence:

- For patients with cUTI or AP: the demonstration that the urine culture grew  $\geq 10^3$  CFU/mL of the baseline strain of ABC identified at study entry and/or a blood culture demonstrates the same baseline pathogen(s), or
- For patients with bacteremia: presence of the baseline strain of ABC on repeat culture.

Patients who are a persistence at EOT will be considered a persistence at TOC.

Microbiologic presumed persistence: no culture was done, and the patient meets clinical criteria for clinical failure.

Microbiologic indeterminate: if clinically indicated (for cUTI and bacteremia only), no follow-up culture is available, the culture cannot be interpreted for any reason, or the culture is considered contaminated.

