The local laboratory will culture each sample for species identification, quantification (urine and BAL only), and susceptibility testing. Any organism isolated from the culture will be identified by genus and species by the local laboratory. Potential pathogen(s) cultured at the local laboratory, including species isolated from mixed infections with other Gram positive or Gram negative organisms, will be sent to a designated central laboratory for confirmation of species identification, susceptibility testing results, and potential molecular characterization.

All organisms identified on culture at the local laboratory and the local laboratory assessment of susceptibility testing for each organism will be captured in the eCRF.

Enrollment in Part A can occur after ABC is identified in the blood and/or other respiratory tract specimens but prior to establishing the resistance profile. If local laboratory susceptibility testing reveals colistin resistance after a patient has been randomized to Part A, the patient must be transferred to Part B, regardless of the treatment group assignment in Part A, once Part B is open for enrollment. If Part B is not open for enrollment, patients will be withdrawn from the study drug treatment.

Patients who are randomized to Part A based on a positive screening of a respiratory sample for ABC by BPP rapid test, but subsequently do not have growth of ABC in their respiratory sample culture processed by the local microbiology laboratory, will be withdrawn from the study drug treatment. The need for continued standard of care treatment should be assessed by the Investigator.

When a patient's culture grows Gram positive organisms but the patient is clinically improving, the patient may remain on study drug without additional Gram positive antibiotic coverage at the Investigator's discretion. Patients who are not clinically improving or need adjustment in antimicrobial therapy that is not allowed per the protocol should be discontinued from study drug at the discretion of the Investigator, but should remain in the study to complete all study assessments. Additional cultures and all EOT procedures should be performed at the time of discontinuation and every attempt must be made to collect survival data at Day 28 or anytime thereafter.

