#### **9.1.2. Handling of Withdrawals and Missing Data**

For the clinical outcome, patients with missing data or who are lost to follow-up will be considered as an indeterminate outcome and are included in the denominator for the calculation of clinical cure rate. Thus, patients with an indeterminate outcome are considered as failures for the analysis. A clinical failure occurring at an earlier time point will be carried forward to the subsequent visits.

In cases of missing or incomplete dates (e.g. AE and concomitant medications), the missing component(s) will be assumed as the most conservative value possible. For example, AEs with missing start dates, but with stop dates either overlapping into the treatment period or missing, will be counted as treatment-emergent, taking the worst-case approach. When partial dates are present in the data, both a partial start date and/or a partial stop date will be evaluated to determine whether it can be conclusively established that the AE started prior to the start of study drug or ended prior to the start of study drug. If the above cannot be conclusively established based on the partial and/or present dates, then the AE will be considered as treatment-emergent. Actual data values as they appear in the original eCRF will be presented in the data listings.

Missing values for other variables will not be imputed and only observed values will be used in data analyses and summaries.

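### Microbiologic persistence is carried from EOT to TOC but not to LFU, so a bacteremia patient cleared by non-study therapy can count as favorable at LFU

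*SAP*

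**What the plan says.** SAP 5.2 lists as a secondary endpoint "Microbiological favorable assessment at EOT, TOC, and LFU in the m-MITT, CRABC m-MITT, ME, and CRABC ME Populations". SAP 9.3.2 repeats it, split into overall, monomicrobial and polymicrobial infection, with 95% CIs for the difference between the arms in Part A.

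For bacteremia, cUTI and AP, SAP 5.5.2.1 assigns the outcome by program from blood and urine cultures:

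- Success: "A microbiological favorable assessment will include eradication and presumed eradications, as detailed below".
- Eradication in bacteremia: "For patients with bacteremia: absence of the baseline strain of ABC on culture". The urinary definition is also a culture threshold. Neither mentions non-study antibiotics or the result at an earlier visit.
- Carry-forward: "Patients who are a persistence at EOT will be considered a persistence at TOC". Protocol 7.8.1 and the Protocol Synopsis have the same sentence.
- Presumed persistence: used only when no culture was done and the patient is a clinical failure.

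The clinical outcome is handled differently. SAP 9.1.2 says: "A clinical failure occurring at an earlier time point will be carried forward to the subsequent visits". The definition of clinical failure in SAP 5.5.1 also refers to non-study treatment: "new symptoms have developed and require the initiation of a non-study Gram negative antibacterial drug therapy".

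Patients who stop study drug are still followed. Protocol 6.6 asks them to complete TOC and LFU. Protocol 7.7 says that patients who are not improving, or who need an antimicrobial change that the protocol does not allow, "should be discontinued from study drug at the discretion of the Investigator, but should remain in the study to complete all study assessments". LFU procedures include blood cultures in bacteremia where applicable (Protocol 6.5) and urine cultures in cUTI and AP (Protocol 7.7.3).

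**The concern.** The microbiologic rule stops one visit short of the clinical rule. At TOC the plan overrides a negative culture once the patient was a persistence at EOT. At LFU it does not, so a negative culture obtained after another drug was started is credited as eradication. The same patient is then a persistence at TOC, a clinical failure at TOC and LFU, and a microbiologic success at LFU.

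For such patients the LFU result reflects the later drug and not the randomized regimen. It also depends on whether a culture was drawn: a negative culture gives a success, and no culture gives presumed persistence. The arm with more rescued and cleared persisters gains more credited eradications, which would blur a real difference at LFU.

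**Working it through.** The plan states no figure on this point, so there is none to reproduce. The check has two parts: running the rules as written, and sizing the effect under stated assumptions.

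**1. Rules as written.** Take a Part A bacteremia patient who is a clinical failure and starts non-study Gram-negative therapy after the first unfavorable result.

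| Culture at EOT / TOC / LFU | As written: EOT / TOC / LFU | LFU if carried forward |
|---|---|---|
| positive / negative / negative | persistence / persistence (carried) / **eradication** | persistence |
| positive / negative / positive | persistence / persistence / persistence | persistence |
| positive / negative / none | persistence / persistence / presumed persistence | persistence |
| negative / positive / negative | eradication / persistence / **eradication** | persistence |
| none / negative / negative | presumed persistence / eradication* / **eradication** | presumed persistence |

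*If the carry-forward sentence covers only culture-proven persistence, which it does not make clear. In that case the gap opens at TOC as well.

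Only the rows with a negative LFU culture change from favorable to unfavorable. With no LFU culture the patient is already unfavorable.

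**2. Whether another rule closes the gap.**

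- Recurrence (SAP 5.5.2.1) needs documented eradication at TOC followed by a positive culture. It does not apply.
- The non-responder rule (SAP 9.3.2) covers missing values. Here a value exists.
- The carry-forward in SAP 9.1.2 is written for the clinical outcome.
- Presumed persistence requires that no culture was done.

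None of them catches the case.

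**3. Size.** Inputs:

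- n = 60 per arm, from 120 CRABC m-MITT patients randomized 1:1 (SAP 4).
- b, the bacteremia share, assumed 10% to 40%. The upper value borrows the Part A cap in Protocol 5.4, which covers HABP, VP and bacteremia together, in all Part A patients whatever their resistance. It is therefore an assumption, not a strict bound for the CRABC m-MITT Population.
- f, the share of bacteremia patients who are persistent, rescued and culture-negative at LFU, assumed 5% to 20%.

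Patients reclassified per arm = n × b × f. Shift in that arm's LFU favorable rate = b × f.

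- Low end: 60 × 0.10 × 0.05 = 0.3 patients; 0.10 × 0.05 = 0.5 points.
- Middle: 60 × 0.20 × 0.10 = 1.2 patients; 0.20 × 0.10 = 2 points.
- High end: 60 × 0.40 × 0.20 = 4.8 patients; 0.40 × 0.20 = 8 points.

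These are shifts in one arm's rate. The difference between arms moves by b × (f in one arm − f in the other). That is zero if the arms are alike, and at most 0.40 × (0.20 − 0.05) = 6 points within these ranges.

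**The case against.** The strongest defense is that LFU may be meant to show the patient's observed microbiologic state, whatever treatment came in between. That is a legitimate endpoint, but the plan does not state it. It also fits poorly with the TOC override, with the clinical carry-forward, and with a rule that makes the same patient unfavorable when no culture is taken.

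The case against a large effect mostly stands. LFU blood cultures are taken where applicable, daily repeats may stop once the patient is a treatment failure (Protocol 7.7.2), and site cultures after screening are taken only when clinically indicated (Appendix A). A patient who dies before an LFU culture cannot be reclassified, and the assumed mortality is 36% to 41%. This is one late visit of one secondary endpoint, with no success criterion attached.

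A reader might go further in three ways that the documents do not support:

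- *Every rescued patient becomes a success at LFU.* No: a negative LFU culture is required.
- *The arm difference shrinks by the share of persisters that rescue clears.* That holds only inside bacteremia, and SAP 9.3.2 does not split this endpoint by infection type. Suppose 8 v 4 persisters: 8/24 − 4/24 = 16.7 points within 24 bacteremia patients per arm, but 8/60 − 4/60 = 6.7 points in the analyzed arm. If 20/60 v 10/60 are unfavorable overall (16.7 points) and half of those bacteremia persisters are cleared, the difference is 16/60 − 8/60 = 13.3 points. That is an attenuation of 20%, not 50%.
- *Urinary patients bias the comparison.* cUTI and AP patients enter only Part B, which has one group and is summarized descriptively.

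**Conclusion.** The gap is real and follows from the text alone. Microbiologic persistence is not carried to LFU, eradication ignores non-study therapy, and no other rule intervenes. A bacteremia patient with persistence at EOT or TOC and a negative LFU culture after rescue is programmed as favorable at LFU. In Part B the same holds for cUTI and AP, where it affects only descriptive rates.

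The comparative consequence is limited to Part A bacteremia patients of that kind, and 28-day all-cause mortality is not affected. The range of 0.5 to 8 points in an arm's LFU favorable rate rests on assumed bacteremia shares and assumed rates of persistence, rescue and clearance, because the documents give none. The upper end needs bacteremia at 40% of the arm, which under the Part A cap leaves no room for HABP or VP if the CRABC m-MITT mix matches Part A. The point is worth correcting before database lock because LFU could otherwise contradict both TOC and the clinical outcome. It does not threaten the trial's main conclusion.

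**What to change.** In SAP 5.5.2.1, Protocol 7.8.1 and the Protocol Synopsis, replace the carry-forward sentence with:

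*Persistence or presumed persistence at EOT is carried forward to TOC and LFU, and persistence or presumed persistence at TOC is carried forward to LFU, whatever a later culture shows.*

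Keep the observed culture results in the listings.

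Do not add a blanket rule that any clinical failure on non-study Gram-negative therapy is microbiologically unfavorable. Clinical failure includes intolerance that leads to stopping study treatment (SAP 5.5.1). Such a rule would turn a switch for intolerance after documented eradication into a microbiologic failure, and tolerability may differ between the arms.

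The cost is one sentence and a small programming change on data already collected; no clinical procedure changes. LFU favorable rates become slightly lower. Two side effects should be accepted openly. A patient who clears late without any rescue stays unfavorable, as the plan already provides at TOC. A patient who stops for intolerance with no EOT culture is presumed persistence at EOT and would now keep that status.

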#### Microbiologic recurrence:

- For patients with cUTI or AP: the demonstration that the urine culture grew  $\geq 10^3$  CFU/mL of the baseline strain of ABC identified at study entry at any time after documented eradication at the TOC Visit up to and including the LFU Visit, or
- For patients with bacteremia: a positive blood culture for ABC at any time after documented eradication at the TOC Visit up to and including the LFU Visit.

### **5.5.2.2. Microbiologic Outcome for Hospital-Acquired Bacterial Pneumonia, Ventilator-Associated Bacterial Pneumonia, Ventilated Pneumonia, or Surgical or Post-Traumatic Wound Infections**

Microbiologic presumed eradication: no culture was done, and the patient meets clinical criteria for clinical cure. For patients with HABP/VABP/VP or surgical or post-traumatic wound infections, where repeat culture samples may not be indicated, presumed eradication based on clinical improvement will be inferred.

Microbiologic presumed persistence: no culture was done, and the patient meets clinical criteria for clinical failure.

## **6. SAFETY ASSESSMENTS**

### **6.1. Adverse Events**

An adverse event (AE) is defined as any untoward medical occurrence in a clinical investigation patient administered a pharmaceutical product, which does not necessarily have a causal relationship with this treatment. An AE can therefore be any unfavorable and/or unintended sign (including an abnormal laboratory finding), symptom, or disease temporally associated with the use of an investigational medicinal product, whether or not related to the investigational medicinal product. All AEs, including observed or volunteered problems, complaints, or symptoms, are to be recorded on the appropriate eCRF. AEs will be coded using the Medical Dictionary for Regulatory Activities (MedDRA, Version 21.0).

### **6.2. Laboratory Assessments**

Standard clinical laboratory profiles for chemistry will be evaluated at Screening, Day 1, Day 3, Day 5, Day 7, the EOT Visit, the TOC Visit, the LFU Visit, and the ET Visit. Serum creatinine will be evaluated daily while the patient is receiving study drug and will be analyzed at the local laboratory to assess the need for dose adjustments. All Screening laboratories will be performed at the local laboratory and may have been collected as standard of care within 48 hours prior to randomization, with the exception of serum creatinine determination, which must be obtained at the local laboratory within 24 hours before the first dose of study drug. All other samples are to be sent to the central laboratory. The Day 5 safety chemistry panel will be performed at the local laboratory and sent to the central laboratory.

Standard clinical laboratory profiles for hematology including complete blood count (with red blood cell count, total white blood cell count with differential counts, platelet count, hemoglobin, and hematocrit) will be performed at Screening, Day 1, Day 3, Day 5, Day 7, the EOT Visit, the TOC Visit, the LFU Visit, and the ET Visit.

A urinalysis including urine dipstick analysis for leukocytes, nitrites, or a catalase test of the urine specimen, microscopic evaluation, specific gravity, and pH will be performed at Screening, Day 1, Day 3, Day 5, Day 7, the EOT Visit, the TOC Visit, the LFU Visit, and the ET Visit.

A highly sensitive urine or serum pregnancy test will be performed at Screening, the EOT Visit, and the ET Visit for women of childbearing potential.

Standard of care safety laboratory profiles should also be performed by the local laboratory. Abnormal values of laboratory parameters must be followed up to normalization or stabilization at the discretion of the Investigator.

### **6.3. Vital Signs**

Vital signs (including systolic and diastolic blood pressure, heart rate, respiratory rate, and, for ventilated patients, oxygen therapy and respiratory settings including fraction of inspired oxygen [FiO2] and positive end-expiratory pressure [PEEP]) will be taken after at least 5 minutes in a seated or supine position. Vital signs will be recorded at Screening, all days that the patient receives study drug treatment, the EOT Visit, the TOC Visit, the LFU Visit, and the ET Visit. Vital signs should be collected at the same time as assessments of signs and symptoms.

